#### **4. Study Procedures**

##### **a. Study design, including the sequence and timing of study procedures:**

No procedures described here are part of routine patient care.

Participants will be selected from a population of women with OUDs in substance use disorder treatment at the Center for Addiction and Pregnancy (CAP), a comprehensive care treatment facility located in Baltimore and providing treatment for substance use disorders, mental health services, obstetric care and pediatrics (Jansson, 1996), which has been the site for all previously described research activities. Additional participants may include stable pregnant patients who are maintained on B+N in treatment by other providers who are willing to leave weekly research urines for toxicology testing and undergo fetal testing procedures. Total subject enrollment will be 160 (80 methadone and 80 B+N) participants; using a conservative estimate of 50% non-completion, the final sample size will be 80 (40 methadone and 40 B+N) mother/infant dyads.

Women accepting or requesting buprenorphine treatment will be offered study participation at the time of their contact with CAP intake staff after indicating a willingness to talk to study staff regarding research. The methadone comparison sample ( $n=80$ ) will be drawn from the population of CAP methadone maintained women and matched on . severity of OUD (route of administration (IV vs other) Eligibility for study enrollment and B+N maintenance will be determined by the project obstetrician and psychiatrist prior to study enrollment. B+N dose after induction to medication will be determined and regulated by the psychiatrist with adjustments made at the recommendation of patient counselors based on subjective and objective indicators of withdrawal or over-medication symptoms. All medication dosing will take place at an observed medication window. Take-home dosing will be afforded for holidays, inclement weather, or at the discretion of the project psychiatrist with input from the subject's counselor for other reasons on an individualized basis. Participants enrolled from other treatment programs will be informed of the study at their treatment program and asked to contact study personnel if they are interested.

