*Infant variables.* Infant testing using the NNNS generates 13 summary scores (habituation, attention, handling, quality of movement, regulation, non-optimal reflexes, asymmetric reflexes, stress/abstinence, arousal, hypertonia, hypotonia, excitability and lethargy) that have been normatively described for both substance exposed and non-exposed infants (Tronick, 2004). Exploratory data analysis techniques will be used to determine distributions for each measure to determine how many of these will be used in the final analysis.

*Breastmilk variables:* Concentrations of B+N and major metabolites in breast milk, maternal and infant plasma

b. Statistical plan including sample size justification and interim data analysis.

*Fetal studies:* Individual analyses will be performed for three cardiac measures (FHR, FHR variability and accelerations) and two motor variables (overall activity, bout duration), and two synthetic measures (event and time series-based FM-FHR coupling, as described in the Procedures section. We will also evaluate effects of BN on maternal physiological function (heart period, respirations, cardiac vagal tone, skin conductance, and blood pressure).

Models for aims 1 and 2 will be longitudinal mixed effects linear regression models with random intercepts (Fitzmaurice, 2011). Additional models with fetal sex interactions will be fit to evaluate whether boys are differentially affected by either exposure, as we have observed in previous evaluating neurobehavior in methadone exposed infants (Jansson, 2010). Additionally, all analyses will be adjusted for maternal age, race, and non-opioid substance use.

For Hypothesis 1A, we will fit a model where the outcome for the  $i$ th individual at the  $j$ th timepoint ( $y_{ij}$ ) =  $\beta_0 + \beta_1 \text{peak} + \beta_2 \text{p}_2 - \text{p}_1 + \epsilon_{ij}$ , and  $\beta_1$  represents the difference, across timepoints, in the outcome between peak and trough measurements. For Hypothesis 1B, we will fit a similar model,  $y_{ij} = \beta_0 + \beta_1 \text{peak} + \beta_2 \text{time} +$

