$\beta_3\text{peak} * \text{time} + \beta_4 \cdot \text{pX4\_p} + \varepsilon_{ij}$ , where  $\beta_3$  represents the rate of change in the difference in outcome between peak and trough over time. For Hypothesis 1C, we will fit a model where  $y_{ij} = \beta_0 + \beta_1\text{peak} + \beta_2\text{BN} + \beta_3\text{peak} * \text{BN} + \beta_4 \cdot \text{pX4\_p} + \varepsilon_{ij}$ , where  $\beta_3$  represents the between-treatment (BN-Methadone) or (BN-Buprenorphine) difference in peak-trough differences. Additionally, we will fit a model with a 3-way interaction between peak, time, and BN to determine if changes over time in peak-trough differences vary between BN and Buprenorphine.

For Hypothesis 2A, we will fit models separately for peak and trough measures where  $y_{ij} = \beta_0 + \beta_1\text{BN} + \beta_2 \cdot \text{pX2\_p} + \varepsilon_{ij}$  where  $\beta_1$  represents the difference in outcome between BN and Bup. We will also fit models where  $(y_{ij}) = \beta_0 + \beta_1\text{BN} + \beta_2\text{time} + \beta_3\text{BN} * \text{time} + \beta_4 \cdot \text{pX4\_p} + \varepsilon_{ij}$ , and  $\beta_3$  represents the difference in outcome trajectory over time between BN and Buprenorphine. For Hypothesis 2B, we will fit a model similar to 2A but only using data from 36 weeks to compare methadone and BN.

*Neonatal study:* For hypothesis 3A, we will use descriptive statistics to characterize NAS in BN-exposed infants, as measured by mean daily NAS scores on days 1-4 of life, highest NAS score, amount of medication (morphine sulfate, mg) required to treat NAS, number of days treated for NAS, and total days hospitalization. For hypothesis 3B, we will fit models of NAS severity (measured by Day 3 Finnegan scores, total medication used to treat NAS, total days of NAS treatment and total days of hospitalization), as a function of BN exposure (compared to methadone exposure), adjusting for maternal age, race, and non-opioid substance use. The models for hypothesis 3C will be analogous, but with buprenorphine exposure as the comparator. For hypothesis 3D, we will examine additional predictors of NAS severity including infant sex (Warren, 2015), daily and cumulative dose of BN, other medications including SSRIs (dosage and categorical), illicit drug use based on number of “dirty” urines and specific substance exposures, cigarette smoking (cigarettes per day and CO levels).

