*Infant study:* For hypothesis 4A, we will use descriptive statistics to characterize BN-exposed infants' NNNS scores on each of 13 summary scales; based on previous work we will focus on habituation, arousal, excitability, and hypertonicity. We will fit a model to determine if NNNS scores change over time during the first month of life, and we will fit an additional model with an interaction between infant sex and time to determine if sex affects NNNS trajectories. For hypothesis 4B, we will fit models where  $\text{NNNS}_{ij} = \beta_0 + \beta_1\text{BN} + \beta_2 \cdot \text{pX2\_p} + \varepsilon_{ij}$ , and  $\beta_1$  represents the difference, across timepoints in the NNNS between BN and methadone exposed infants. We will then fit a model where  $\text{NNNS}_{ij} = \beta_0 + \beta_1\text{BN} + \beta_2\text{time} + \beta_3\text{BN} * \text{time} + \beta_4 \cdot \text{pX4\_p} + \varepsilon_{ij}$ , where  $\beta_3$  represents the difference in NNNS trajectories over time between BN and methadone-exposed infants. For hypothesis 4C, we will fit analogous models to 4B, but with buprenorphine-exposed infants as the comparator. These models will be adjusted for maternal age, race, dosing, and other substance use.

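### Route of opioid use (IV vs other) is the only legible matching factor for the methadone group but is in no listed covariate set, so balance on it is not assured among the women analysed

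*Combined protocol and SAP*

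**What the plan says.** Section 4a says that the methadone comparison sample "will be drawn from the population of CAP methadone maintained women and matched on" a factor given as "severity of OUD (route of administration (IV vs other"). The sentence is damaged: a stray full stop precedes the factor and a bracket is never closed, so another factor may have been lost. Route is the only one that can be read. No ratio, method (individual or frequency), replacement rule or balance check is given.

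The same section allows B+N women from outside CAP: "Additional participants may include stable pregnant patients who are maintained on B+N in treatment by other providers". It makes no such provision for methadone women. On loss it states: "using a conservative estimate of 50% non-completion, the final sample size will be 80 (40 methadone and 40 B+N) mother/infant dyads".

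The covariates are in section 7b:
- Fetal models (Aims 1 and 2): "all analyses will be adjusted for maternal age, race, and non-opioid substance use".
- NAS models (hypotheses 3b and 3c): "adjusting for maternal age, race, and non-opioid substance use".
- NNNS models (Aim 4): "These models will be adjusted for maternal age, race, dosing, and other substance use".

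Route is in none of these lists, in no written equation, and not among the exploratory NAS predictors of hypothesis 3d. The 2012-2016 buprenorphine-only group is called historical and never matched. Section 3 says only that the earlier projects recruited from CAP under essentially the same eligibility criteria.

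**The concern.** The arms are not randomised. The plan picks one marker of severity as important enough to control by design, then does not carry it into the analysis. Matching at enrolment governs the 80 and 80 women who enter. The comparisons rest on those who supply data, projected as 40 and 40 completers.

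Loss that depends on route differently in the two arms would undo the balance, and the plan's own text makes this plausible. Opioid use during B+N induction may lead to removal (section 4a). Disliking B+N, B+N side effects and missed B+N dosing are named grounds for leaving (section 4f). Attrition during induction is named in section 7c. Methadone women face none of these, and stable B+N women from other providers skip induction.

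For the buprenorphine-only contrasts, balance on route was never created. A difference in severity could then appear as a drug effect on fetal measures, NAS or NNNS. Where similarity is expected (3c, 4c), it could also hide a real difference.

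**Working it through.** **1. The plan's own figures.** Inputs from section 7b: power 0.80, alpha 0.05 (taken as two-sided, which is not stated), 40 per group. Formula: n per group = 2 × (1.960 + 0.842)² / d².
- Hypothesis 1: d = 4.23/6.68 = 0.633, n = 40.
- Hypothesis 2: d = 4.12/6.49 = 0.635, n = 39.
- Hypothesis 3: d = 0.63, n = 40.
- Hypothesis 4: d = 0.44/0.70 = 0.629, n = 40.

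Enrolment: 40/(1 − 0.5) = 80 per arm, 160 in all. The stated figures reproduce, so the detectable difference is about 0.63 SD.

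**2. Does 50% loss upset balance on route?** Let p be the IV share at enrolment, equal in both arms by matching. The IV share among completers is p·c_IV / (p·c_IV + (1 − p)·c_other), where c_IV and c_other are completion rates by route. All of these are assumptions. Take p = 0.5.
- Same pattern in both arms (40% IV, 60% other): 0.20/(0.20 + 0.30) = 0.40 in each. Gap 0.
- B+N 40%/60%, methadone 50%/50%: 0.40 against 0.50. Gap 10 points.
- B+N 40%/60%, methadone 60%/40%: 0.40 against 0.60. Gap 20 points.

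Overall completion is 50% in every case. The size of the loss does not break the balance; a difference between arms in how loss depends on route does.

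Purely random loss adds chance imbalance. The SD of the gap is √(2 × 0.25/40 × 40/79) = 0.08, against √(2 × 0.25/40) = 0.11 for two unmatched groups of 40. The matching still helps in that case.

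**3. Size of bias without adjustment.** Bias = gap in IV share × effect of route in SD units. The route effect is assumed to be 0.3 to 0.8 SD.
- Methadone contrasts, gap 10 to 20 points: 0.10 × 0.3 = 0.03 SD to 0.20 × 0.8 = 0.16 SD.
- Historical contrasts, assumed gap 10 to 30 points: 0.10 × 0.3 = 0.03 SD to 0.30 × 0.8 = 0.24 SD.

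**4. What that does to a test.** With 40 per group the standard error is √(2/40) = 0.224 SD. A bias of 0.15 SD shifts the test statistic by 0.15/0.224 = 0.67 and raises the two-sided false-positive rate from 5% to about 10%. A bias of 0.24 SD shifts it by 1.07, giving about 19%.

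**5. Cost of adjusting.** At d = 0.63 and 40 per group, power is 0.80 (normal) or 0.79 (t-test), and one degree of freedom barely changes it. If IV shares were 40% and 60%, the correlation between group and route would be 0.2 and the standard error would grow by 1/√(1 − 0.04) = 1.02, before any gain from variance that route explains.

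**6. Which term is needed.** In 1c the tested term is peak × BN, a contrast within women. A route main effect shifts a woman's peak and trough values together and hardly touches that term; route × peak is needed. Likewise, the trajectory models test BN × time and need route × time. The within-woman contrasts 1a and 1b are not between-group comparisons and are outside this point.

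**The case against.** The strongest case against runs as follows.
- **Losing half of each group does not unbalance a group-level match.** This stands. The plan shows no difference in completion by route, so the most that can be said is that balance is not assured.
- **The matching sentence is damaged.** This also stands. Route cannot be called the sole matching factor, only the sole legible one.
- **Every input to the bias is assumed, and the result is small beside 0.63 SD.** True. No section links route to any outcome. The range shows what is at stake and is not an estimate.
- **The analysis need not be confined to completers.** Random-intercept models can use visits from women who later leave, and women who relapse are not disenrolled. This stands for most fetal models. It helps less for 2b, which uses 36-week data only.
- **The plan leaves room for route.** Section 7b says its analyses are not exhaustive, and section 4a speaks of controlling for confounders. Neither commits to this covariate, and use of other substances does not stand in for the route by which opioids were taken.
- **Route may be unavailable for the 2012-2016 cohort.** No section says that it was recorded, so the remedy there must be conditional.

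A reader might also multiply 50% by 50% and infer that only a quarter of matched pairs survive. The documents do not support this. They speak of a matched sample and a matched cohort, and nowhere of individual pairs or a pair-based analysis.

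**Conclusion.** The point holds as a cheap improvement. The plan's one legible matching factor and severity marker is missing from every between-group model, and the historical contrasts have no stated control for it.

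The bias is about 0.03 to 0.24 SD, if IV shares differ by 10 to 30 points and route shifts the outcome by 0.3 to 0.8 SD. It is zero in expectation for the methadone contrasts if completion by route is the same in both arms. Even the upper end is well below the detectable 0.63 SD, though it would matter for a borderline result or a claim of similarity.

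A reader might infer that the matching has failed, or that dropout destroys it. The documents support neither reading.

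**What to change.** - State the matching factors, ratio and method in section 4a.
- Add enrolment route (IV vs other) as a covariate in the prospective between-group models: the methadone part of 1c, 2b, 3b and 4b.
- Do the same in the historical contrasts (the buprenorphine part of 1c, 2a, 3c and 4c) if route was recorded for that cohort. If it was not, state that these contrasts are not controlled for route.
- Where the tested term is an interaction, add the corresponding route term: route × peak in 1c, route × time in the trajectory models. For the three-way peak, time and BN model, state how route enters.
- Tabulate route by group among women enrolled and among women analysed.

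For the prospective women nothing new need be collected, because route must be known in order to match on it. The cost is one or two degrees of freedom per model, with power still about 79-80% at 40 per group and no change in sample size. For the historical cohort there is the work of checking whether route can be retrieved.

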### **Maternal-fetal monitoring protocol**

[figure not shown]
[figure not shown]
Maternal-fetal monitoring will occur at the 24th, 28th, 32nd and 36th weeks of gestation. These periods reflect the most intensive developmental trajectories in fetal neurobehaviors, which become more complex as term advances, with a shift in the steepness of the developmental trajectory in most parameters between 28 and 32 weeks ([name], 2004). Quality continuous fetal heart rate monitoring is difficult prior to 24 weeks due to movement artifact. Monitoring sessions will last for 60 minutes and be conducted at 9 AM (the time of trough maternal B+N level) and again at 2 ½ hours after a single sublingual dose of B+N which corresponds to the time of peak maternal medication level. Women who are recruited for study participation will have their dose administered around 10 AM for 1 week prior to the time of fetal testing, and be on a stable dose of B+N during that time period. On the day of fetal testing, women will be instructed to eat breakfast 1 ½ hours prior to testing to control variation in blood glucose. Concurrent maternal-fetal monitoring will be digitized at 1000 Hz using an external analog to digital board using streaming software (Snapstream, HEM, Inc). The methodology and data processing techniques described have been used in our prior studies and are comprehensively described elsewhere ([name], 2015).

*Fetal data.* Fetal data will be generated from a Toitu (MT516) fetal actocardiograph, which detects fetal movement (FM) and fetal heart rate (FHR) through a single wide array transabdominal Doppler transducer and processes this signal through a series of filtering techniques. The actograph detects FM by preserving the remaining signal after band-passing frequency components of the Doppler signal that are associated

with FHR and maternal somatic activity. Reliability studies comparing actograph-based to ultrasound-visualized FMs have found this monitor to be accurate (Besinger & Johnson, 1989; [name], 1999; Maeda, 1999). Data will be analyzed off-line using software developed by [name] (GESTATE; James Long Company, Caroga Lake, NY). A series of algorithms will be applied to detect physiologically improbable changes in FHR while maintaining the temporal nature of the data, using serial expansion and contraction of acceptable limits in progressive intervals, based on moving averages (medians) of preceding data points. FM data represent raw voltage values generated from the actograph, calibrated by multiplying by a conversion factor with adjustment for offset, and scaled from 0 to 100 in arbitrary units. Derived fetal variables include those centered on heart rate alone, movement, and their interrelation. Cardiac variables will include FHR, FHR variability (root mean square) and FHR accelerations (i.e., episodic excursions in FHR amplitude above baseline). Movement is characterized as number of bouts, duration, and total motor activity. Linkage between the two domains of function will be quantified through ascertaining the degree to which there is somatic-cardiac (FM-FHR) coupling based on a priori criteria (i.e., the proportion of observed FMs associated with excursions in FHR of a predetermined criteria for a predetermined length of time; ([name], 1996) and the temporal linkage between the two, computed in seconds ([name], 2001). FM-FHR coupling reflects coactivation of the sympathetic and parasympathetic components of the autonomic nervous system since changes in heart rate and movement are temporally, but not necessarily causally related, leading to the conclusion that the two activities are centrally coordinated (Timor-Tritsch, 1978) with a predictable developmental trajectory during gestation.

*Maternal data.* Maternal physiologic signals will be amplified using a multi-channel, electrically isolated, bioamplifier. Electrocardiogram will be recorded from 3 carbon fiber disposable electrodes in triangulated placement; data will undergo R-wave detection, manual editing for artifact, and quantified as heart period (interval between R-waves in msec), heart period variability (standard deviation of successive heart periods), and an indicator of respiratory sinus arrhythmia which reflects vagal, predominantly parasympathetic influences on heart rate variation (Grossman & Kollai, 1993). Vagal tone will be indexed using the analytic technique developed by Porges (1986), which applies a 21-point polynomial to detrend sequential heart periods and a band-pass filter to extract the variance within the frequency band consistent with respiration within this age group (i.e., 24 to 1.04 Hz). Electrodermal activity (skin conductance) will be monitored from two electrodes with gelled skin contact area placed on the distal phalanxes of the index and middle fingers of the non-dominant hand affixed with adhesive. Skin conductance will be measured by administering a constant 0.5 volt root-mean-square 30 Hz AC excitation signal and detecting the current flow; scaling will be from 0 to 25 microsiemens. Respiratory data will be collected via a bellows gauge and quantified in terms of period (sec between breaths). Maternal data will be time synchronized and analyzed in conjunction with fetal data using the GESTATE program. Blood pressure will be measured at the start of each session using a sphygmomanometer. All maternal and fetal measures, with the exception of blood pressure, will be computed in 1-minute intervals and averaged over the 60 min recording.

Below are a schematic of the maternal-fetal monitoring system (left) and raw output values (right).

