Study duration and the number of study visits depends on when during gestation (up to 34 weeks of gestational age) the participant enters the protocol. One hour long maternal-fetal monitoring sessions will occur up to 8 times, twice on 4 separate days at monthly intervals (i.e., 24, 28, 32 and 36 weeks). The number of monitoring visits depends on the gestational age at enrollment; participants enrolling after 24 weeks will have fewer visits. There are no study visits for neonatal testing, as all data are abstracted from neonatal charts as standard of care. Infants will be enrolled for 1 month after birth, and make 3 study visits (days 3, 14 and 30). For those participants enrolled in the lactation arm, study visits will occur on days 2,3,4,14 and 30 postpartum for sampling.

c. Blinding, including justification for blinding or not blinding the trial, if applicable.

This trial is not an open label trial; therefore, there is no blinding of study participants.

d. Justification of why participants will not receive routine care or will have current therapy stopped.

All CAP participants will receive standard substance use disorder, prenatal and pediatric care through the CAP program and in the newborn nursery or NICU. All participants from other treatment programs will receive care through their providers in those programs.

e. Justification for inclusion of a placebo or non-treatment group. NA

f. Definition of treatment failure or participant removal criteria.

There are several scenarios under which participants may terminate the study voluntarily or as a result of safety or compliance concerns. These include: patient choice (e.g., does not like buprenorphine-naloxone); voluntary or enforced discharge from the CAP or other treatment program (e.g., from incarceration, relocation, violation of CAP rules); physician choice (e.g., toxicity or side effects related to buprenorphine-naloxone); and ineligibility (e.g., violation of the study protocol, missing 5 consecutive days of buprenorphine-naloxone dosing, loss of pregnancy, development of fetal or maternal health condition).

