## **7. Study Statistics**

- a. Primary outcome variable.

*Fetal variables.* Derived fetal variables include those centered on heart rate alone, movement, and their interrelation. Cardiac variables will include FHR, FHR variability (root mean square) and FHR accelerations (i.e., episodic excursions in FHR amplitude above baseline). Movement is characterized as number of bouts, duration, and total motor activity. Linkage between the two domains of function will be quantified in two ways: somatic-cardiac (FM-FHR) coupling based on a priori criteria (i.e., the proportion of observed FMs associated with excursions in FHR of a predetermined criteria for a predetermined length of time; ([name], 1996) and through time series techniques to quantify linkage without a priori criteria ([name], 2001). With the exception of accelerations, motor bouts, and somatic-cardiac coupling which are either counts or proportions. Variables are quantified in 1-minute epochs and mean values for each 60 minute recording are used for analysis. Fetal measures will be derived at trough (just prior to dosing) and peak (2 hours after dosing) maternal buprenorphine levels.

*Maternal autonomic variables.* Maternal ECG data will undergo R-wave detection, manual editing for artifact, and quantified as heart period (interval between R-waves in msec), heart period variability (standard deviation of successive heart periods), and an indicator of respiratory sinus arrhythmia which reflects vagal, predominantly parasympathetic influences on heart rate variation (Grossman & Kollai, 1993). Maternal variables also include respiratory period (s) and skin conductance. As with the fetal data, variables are quantified in 1-minute epochs and mean values for each 60 minute recording are used for analysis.

*Neonatal variables.* The primary newborn study measures are Neonatal Abstinence Syndrome (NAS) scores as assessed every four hours for the duration of the infant's hospital stay after delivery. Variables will include mean NAS scores on days 1 through 4 minimally (all opioid exposed infants are hospitalized for a minimum of four days after delivery for observation) or for the infant's hospitalization, and highest score. NAS severity will also be quantified as the total amount of medication (oral morphine sulfate, mg) used to treat NAS, days of pharmacologic treatment required, and total days of hospital stay.

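### For B+N women the trough recording always comes first in the morning and the peak recording always follows around midday, so the Hypothesis 1a peak coefficient cannot be attributed to drug level alone

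*Combined protocol and SAP*

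**What the plan says.** Section 4a (Maternal-fetal monitoring protocol) has the recordings "conducted at 9 AM (the time of trough maternal B+N level) and again at 2 ½ hours after a single sublingual dose of B+N". It adds that "Monitoring sessions will last for 60 minutes" and that recruited women "will have their dose administered around 10 AM for 1 week prior to the time of fetal testing". Section 4b places both recordings on one day: "One hour long maternal-fetal monitoring sessions will occur up to 8 times, twice on 4 separate days at monthly intervals".

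On food, section 4a says only that on the testing day "women will be instructed to eat breakfast 1 ½ hours prior to testing to control variation in blood glucose".

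Section 7a times the recordings differently: "Fetal measures will be derived at trough (just prior to dosing) and peak (2 hours after dosing) maternal buprenorphine levels".

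Hypothesis 1a (section 2) predicts that fetal heart rate and motor patterns are attenuated when circulating medication is at its peak. In section 7b the quantity that tests it is the coefficient on peak, which "represents the difference, across timepoints, in the outcome between peak and trough measurements". All analyses are adjusted for the mother's age, her race and her use of non-opioid substances. No term for clock time, session order or meals is listed. Section 4e marks a placebo or untreated group as not applicable.

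**The concern.** Hypothesis 1a is a statement about drug level, tested by comparing two recordings that differ in more than drug level. Under the B+N schedule the pre-dose recording is always first and in the morning, and the post-dose recording is always second and around midday. The plan itself treats blood glucose as something to control, yet it times one meal relative to testing and says nothing about eating before the second recording.

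If fetal heart rate or movement shifts over the morning for any other reason, the peak coefficient absorbs that shift. Aim 1 could then report a time-of-day, order or meal effect as fetal attenuation by the medication. A shift in the other direction could hide a real effect. More participants do not help; they estimate the same mixture more precisely.

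**Working it through.** **1. Timing (inputs: sections 4a and 7a).**

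| | Peak at 2.5 h (section 4a) | Peak at 2 h (section 7a) |
|---|---|---|
| Trough start | 9:00 | 9:00 |
| Peak start | 10:00 + 2.5 h = 12:30 | 10:00 + 2 h = 12:00 |
| Gap between starts | 3.5 h | 3.0 h |
| Breakfast, if timed to the 9 AM recording | 7:30 | 7:30 |
| Time since breakfast at trough | 1.5 h | 1.5 h |
| Time since breakfast at peak, if nothing is eaten in between | 5.0 h | 4.5 h |

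The last row is conditional, because the documents do not say whether women eat between recordings.

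**2. Can the analysis separate the parts?** Code peak as 0 or 1. At the section 4a times:
- clock time = 9 + 3.5 × peak
- order = 1 + peak
- hours since breakfast = 1.5 + 3.5 × peak (nothing eaten in between)

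A design matrix with columns for intercept, peak, clock time, order and hours since breakfast has 5 columns and rank 2, so no adjustment can split them. The listed covariates describe the woman. They are essentially the same at both recordings of a day and cannot absorb a within-day shift.

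Real start times will vary. If they vary about schedule with SD s hours (an assumption), the variance inflation for peak given clock time is 1 + (3.5/2)²/s²:
- s = 0.25 h: 1 + 3.0625/0.0625 = 50
- s = 0.5 h: 1 + 3.0625/0.25 = 13.25

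Order stays exactly tied to peak however much start times vary.

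**3. The plan's own figure.** Section 7b states 80% power for a peak/trough heart-rate difference of 4.23 (SD 6.68). A two-sided, two-sample t-test at 0.05 with 40 per group gives power 0.799, so the figure reproduces as a comparison of two independent groups. The documents do not say whether 6.68 is the SD of a paired difference or of a single recording. No sample-size figure is disputed here.

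**4. Illustration of size.** Assume no drug effect, one pair per woman and 6.68 as the SD of the paired difference. The standard error with 40 women is 6.68/√40 = 1.056. A pure non-drug shift d gives a paired t-test with noncentrality d/1.056, which is 1.89 for d = 2. The chance that 1a is significant (two-sided 0.05):

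| Shift (bpm, assumed) | 40 women | 80 women |
|---|---|---|
| 1 | 15.2% | 26.2% |
| 2 | 45.5% | 75.3% |
| 3 | 79.1% | 97.8% |

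The 80-women column also assumes that methadone women follow the same schedule, which the documents do not state.

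If 6.68 is instead a single-recording SD with within-woman correlation r (assumed), the SD of the difference is 6.68 × √(2(1 − r)): 7.90 at r = 0.3 and 5.17 at r = 0.7. A 2 bpm shift then gives about 35% to 66% with 40 women, and 61% to 93% with 80.

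**5. Hypotheses 1b and 1c.** The 1b coefficient is peak by gestational time. A session shift that is constant from 24 to 36 weeks drops out; one that changes with gestation stays in. The 1c coefficient is a between-group difference in peak-trough differences. A shift common to the groups cancels if they are tested on the same schedule.

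**The case against.** The strongest reply has four parts.

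- **Order is unavoidable under this schedule.** With a dose at about 10 AM, a same-day pre-dose recording must come before the peak. That is true, and it is why the main remedy concerns what the coefficient is said to estimate.

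- **No fasting is prescribed.** A reader might infer that women are fasting by the peak recording. The documents do not say so; food between recordings is simply not addressed. The smoking rule in section 4a is tied to each recording and the breakfast rule is not, so the natural reading is that breakfast is timed to the first. The supportable point is an uncontrolled meal state. The time-of-day and order problem does not depend on it.

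- **Adding a meal could do harm.** The buprenorphine-only comparator is historical (section 1), and section 3 says all the group's studies used the same assessment paradigm. If the historical women had no meal before the second recording (their rule is not given), a new meal for current participants would create a meal difference between groups at peak. This stands and limits the fix.

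- **The percentages are not error rates for this plan.** Also right. The shift sizes are assumed, the planned model uses up to four test days rather than one pair, and the meaning of 6.68 is unstated.

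Two further inferences are tempting. One is that 1b carries the same mixture as 1a; it does so only for a session effect that varies with gestation. Section 4a describes marked developmental change over these weeks, so constancy cannot be taken for granted, but no such variation is shown. The other is that 1c can carry the acute-effect claim in place of 1a. Every group in 1c is dosed, so it identifies a difference between drugs. If two drugs attenuated the fetus equally, 1c would be zero although both acted.

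**Conclusion.** The point holds for Hypothesis 1a in B+N women. As scheduled, the peak coefficient is inseparable from time of day and session order, it carries an uncontrolled difference in time since eating, and no listed covariate can remove this. It supports a statement about the two sessions, not about circulating drug alone. This conclusion needs only the stated schedule and model, and it is the same whether peak is 2 or 2.5 hours after the dose.

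The size is unknown. The 46% figure for a 2 bpm shift with 40 women rests on an assumed shift, no drug effect, one pair per woman and 6.68 as the paired SD. It shows that a modest shift could matter, not that one exists.

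The fixed order is documented only for B+N. Hypothesis 1a also covers methadone, but no methadone dosing or session times are given. A reader might extend the finding to every woman in the trial, or assume that a shared shift cancels in 1c; the documents support neither until that schedule is stated.

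**What to change.** 1. In section 7b, define the 1a coefficient as a peak-versus-trough session difference that includes time of day, order and meal state, and do not attribute it to drug level alone. Apply the same caveat to 1b for any session effect that changes with gestation. State that 1c estimates a between-drug difference.
2. Record the actual start time and the time since last food at every recording, and report 1a with a sensitivity adjustment for time since last food. This informs only as far as eating times actually vary; it cannot separate order.
3. Standardize the meal interval before the second recording only if that matches how the historical buprenorphine cohort was tested. Otherwise keep the procedure the same across groups.
4. Reconcile the 2-hour peak time in section 7a with the 2.5-hour time in section 4a, and state the session schedule for the methadone group.

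The cost is a weaker claim from 1a and two extra items recorded per session. No visits or participants are added.
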